6 STUDY TREATMENTS

Study treatment is defined as any investigational product(s) intended to be administered to a study participant according to the study protocol. Study treatment in this study refers to MEDI9447.

6.1 Treatments administered

6.1.1 Investigational products

Table 6 Investigational Product

Investigational Product	Concentration and Formulation as Supplied
MEDI9447	Supplied as a solution for infusion containing 500 mg of MEDI9447 50 mg/mL per vial

The sponsor will provide study drugs as shown in [Table 6](#).

The sponsor will provide MEDI9447 as concentrate for solution for infusion containing 500 mg of MEDI9447 per vial. The solution contains 50 mg/mL MEDI9447 in 25 mM histidine/histidine hydrochloride, 240 mM sucrose, 0.03% (weight/volume [w/v]) polysorbate 80; it has a pH of 6.0. The nominal fill volume is 10.0 mL.

Vials should be stored at 2°C to 8°C and not be frozen. Drug product should be kept in secondary packaging until use to prevent excessive light exposure.

See [Figure 1](#) as for dosing for each cohort.

Labels will be prepared in accordance with Good Manufacturing Practice (GMP) and Good Clinical Practice (GCP) Ordinance. Details are specified in the document explaining the reconstitution procedures and other handling procedures for the investigational products.

6.2 Preparation/ handling/ storage/ accountability

Each vial selected for dose preparation should be inspected. If any defects (if the solution is turbid or if any discoloration etc.) are noted with the investigational product(s), the sponsor should be notified immediately and the vial(s) should be stored in QUARANTINE at 2°C to 8°C.

After removing the required number of vials for dose preparation (3 vials for the 1500 mg dose; 6 vials for the 3000 mg dose) from the carton container, the carton should be immediately returned to storage at 2°C to 8°C.

MEDI9447 doses must be prepared by the investigator's or site's designated investigational product manager using aseptic technique. Total time from needle puncture of the MEDI9447 vial to the start of administration should not exceed: 24 hours at 2°C to 8°C, 4 hours at room temperature. If preparation time exceeds the time limits a new dose must be prepared from new vials. MEDI9447 does not contain preservatives, and any unused portion must be discarded.

Doses of MEDI9447 1500 mg and 3000 mg will be administered using an IV bag containing 0.9% (w/v) saline, with a final MEDI9447 concentration ranging from 1.5 to 30 mg/mL, and delivered through an IV administration set with a 0.2- or 0.22- μ m in-line filter. An IV bag made of polyolefin or polyvinylchloride should be used. Add 30 mL (i.e., 1500 mg dose) or 60 mL (i.e., 3000 mg dose) of MEDI9447 to the IV bag. The IV bag size should be selected such that the final concentration is within 1.5 to 30 mg/mL. Mix the bag gently to ensure homogeneity of the bag. MEDI9447 will be administered at room temperature by controlled infusion into a peripheral or central vein. Standard infusion time for MEDI9447 is 1 hour; however, if there are interruptions during infusion, the total allowed time should not exceed 4 hours at room temperature. If this duration is met, then the remainder of the dose should be abandoned and should not be completed with a second prepared dose. Do not co-administer other drugs through the same infusion line. Flush the IV line with a volume of IV diluent equal to the priming volume of the infusion set used after the contents of the IV bag are fully administered, or complete the infusion according to institutional policy to ensure the full dose is administered and document if the line was not flushed.

The investigator or designee must confirm appropriate temperature conditions have been maintained during transit for all study treatment received and any discrepancies are reported and resolved before use of the study treatment.

Only subjects enrolled in the study may receive study treatment and only authorized site staff may supply or administer study treatment. All study treatments must be stored in a secure, environmentally controlled, and monitored (manual or automated) area in accordance with the labelled storage conditions with access limited to the investigator and authorized site staff.

The investigator, institution, or the head of the medical institution (where applicable) is responsible for study treatment accountability, reconciliation, and record maintenance (i.e., receipt, reconciliation, and final disposition records).

Further guidance and information for the final disposition of unused study treatment are provided in the study drug handling instructions.

6.3 Measures to minimise bias: randomisation and blinding

This is an open-label, non-randomised study.

6.4 Treatment compliance

Any change from the dosing schedule, does interruptions, dose discontinuations should be recorded in eCRF.

The Investigational Product Storage Manager is responsible for managing the investigational product from receipt by the study site until the destruction or return of all unused investigational products.

6.5 Concomitant therapy

Any medication or vaccine (including over-the-counter or prescription medicines, vitamins, and/or herbal supplements) that the subject receives from signing of the ICF to 90 days after the last dose of study treatment must be recorded along with:

- Reason for use
- Dates of administration including start and end dates
- Dosage information including dose and frequency

6.5.1 Permitted concomitant therapies

Investigators may prescribe concomitant medications or treatments (e.g., acetaminophen, diphenhydramine) deemed necessary to provide adequate prophylactic or supportive care except for those medications identified as “excluded” as listed in Section 6.5.2.

6.5.2 Prohibited concomitant therapies

Subjects must be instructed not to take any medications, including over-the-counter products, without consulting with the investigator.

The use of following medications are prohibited during the study. The sponsor must be notified if a subject receives any of these during the study.

- 1 Other investigational products
- 2 Any concurrent chemotherapy, radiotherapy (except palliative radiotherapy), immunotherapy, biologic or hormonal therapy for cancer treatment. Bisphosphonates or denosumab for bone metastases can be used on a fixed dosing during the study only if the subjects have been on the medication prior to signing the ICF. Concurrent use of hormones for non-cancer-related conditions (e.g., insulin for diabetes and hormone replacement therapy) is acceptable
- 3 Immunosuppressive medications including, but not limited to systemic corticosteroids at doses exceeding 10 mg/day of prednisone (or prednisolone, which is available in Japan in place of prednisone) or equivalent, methotrexate, azathioprine, and tumor necrosis factor-alpha blockers. Use of immunosuppressive medications for the management of investigational product-related AEs or in subjects with contrast allergies is acceptable. In addition, use of inhaled, topical and intranasal corticosteroids is permitted. Temporary use of corticosteroids for treatment of underlying or concurrent illness or in the setting of palliative radiotherapy may be permitted upon discussion with the Study Physician.
- 4 Prophylactic antiemetic premedication for nausea or granulocyte colony stimulating factors is not permitted during the DLT Evaluation period (therapeutic use of anti-emetics and granulocyte colony stimulating factor is allowed.)
- 5 Live attenuated vaccines during the study through 30 days after the last dose of study drug. Vaccination with a killed vaccine is permitted at any time with consultation with the Study Physician.
- 6 Herbal and natural remedies including Chinese medicine should be avoided

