5 STUDY POPULATION

Investigators should keep a record (i.e., patient screening log) of patients who entered pre-study screening.

Each patient must meet all of the inclusion criteria and none of the exclusion criteria for this study at the time of allocation in each cohort of the study. Under no circumstances can there be exceptions to this rule.

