 - Hypothyroidism (e.g., following Hashimoto syndrome) which is stable on hormone replacement or psoriasis not requiring systemic treatment.
- 15 Untreated or unstable central nervous system (CNS) metastatic disease, leptomeningeal disease, or cord compression. Note: Subjects previously treated for CNS metastases that are radiographically and neurologically stable for at least 4 weeks prior to the first dose of study drug and do not require corticosteroids (of any dose) for symptomatic management for at least 14 days prior to the first dose of study drug are not excluded.
- 16 Concurrent enrollment in another clinical study, unless it is an observational (non interventional) clinical study or the follow-up period of an interventional study
- 17 Any concurrent chemotherapy, immunotherapy, or biologic or hormonal therapy for cancer treatment. Concurrent use of hormones for noncancer-related conditions (e.g., insulin for diabetes and hormone replacement therapy) is acceptable. In addition, local treatment (e.g., with a local surgery or radiotherapy) of isolated lesions for palliative intent is acceptable beyond the DLT-evaluation period with prior consultation and in agreement with the Study Physician.
- 18 Toxicities from prior anticancer therapy that have not resolved to \leq NCI CTCAE v4.03 Grade 1 or baseline prior to the first dose of study drug, with the exception of alopecia and laboratory values per inclusion criteria. The eligibility of patients who are still experiencing irreversible toxicity that is not reasonably expected to be exacerbated by the study drugs in this study (e.g., hearing loss) must be reviewed and approved by both the Principal Investigator and the Study Physician.
- 19 History of primary immunodeficiency or solid organ transplantation

- 20 Active hepatitis B (known positive hepatitis B virus [HBV] surface antigen (HBsAg) result), hepatitis C, or human immunodeficiency virus (HIV) (positive HIV 1/2 antibodies). Patients with a past or resolved HBV infection (defined as the presence of hepatitis B core antibody [anti-HBc] IgG and absence of HBsAg and HBV deoxyribonucleic acid [DNA]) are eligible. Patients positive for hepatitis C virus (HCV) antibody are eligible only if polymerase chain reaction is negative for HCV ribonucleic acid (RNA).

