6.6.2 Definition of dose-limiting toxicity and evaluable subject

DLT evaluable patients are defined as those who received 2 planned doses of MEDI9447 per protocol during the DLT assessment period and completed the safety follow-up through the DLT assessment period, or those who experienced a DLT. Also, the period for DLT evaluation is defined as the time from receiving the first dose of investigational product until assessments prior the planned administration of the third dose; this corresponds to 28 days after receiving the first dose of the investigational product or 14 days after the second dose, whichever occurs later (defined as Cycle 1). Subjects who do not remain in the study up to this time for reasons other than DLT will be considered non-evaluable for DLT assessment and will be replaced with another subject at the same dose level. In case of discontinuation from or interruption of treatment due to AE during the DLT evaluation period (e.g., \geq grade 3 IRR), whether the AE should be a DLT will be discussed by the SRC based on the below mentioned DLT definition 11. Grading of DLTs will be according to the NCI CTCAE v4.03.

A DLT will be defined as any of the events listed below that occurs during the DLT-evaluation period (defined above). Toxicity that is clearly and directly related to the primary disease or to another etiology is excluded from this definition. The following will be DLTs:

- 1 Grade 4 immune-mediated adverse event (imAE)
- 2 \geq Grade 3 colitis
- 3 \geq Grade 3 nausea, vomiting, or diarrhea that does not resolve to Grade 2 or less within 3 days of the initiation of maximal supportive care
- 4 \geq Grade 3 pneumonitis or ILD
- 5 Grade 4 anemia or anemia requiring red cell transfusion
- 6 Grade 4 thrombocytopenia or neutropenia that is present for more than 4 days
- 7 Grade 3 thrombocytopenia with bleeding or thrombocytopenia requiring platelet transfusion

- 8 Febrile neutropenia
- 9 Isolated liver transaminase elevation $\geq 5 \times$ but $\leq 8 \times$ ULN or isolated total bilirubin $\geq 3 \times$ but $\leq 5 \times$ ULN that does not downgrade to Grade 2 or less within 14 days after onset with optimal medical management, including systemic corticosteroids. Isolated liver transaminase elevation $> 8 \times$ ULN or isolated total bilirubin $> 5 \times$ ULN regardless of duration.

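### Section 6.5.2 item 2 exempts palliative radiotherapy from the on-study ban without the DLT-period limit or the Study Physician agreement that exclusion criterion 17 requires

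*Supplement*

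**What the plan says.** Two places in the protocol deal with palliative radiotherapy for a subject on treatment.

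- **Section 5.2, exclusion criterion 17.** Local treatment, with surgery and radiotherapy as the named examples, "of isolated lesions for palliative intent is acceptable beyond the DLT-evaluation period with prior consultation and in agreement with the Study Physician".
- **Section 6.5.2, item 2.** The list opens with "The use of following medications are prohibited during the study", and item 2 covers "Any concurrent chemotherapy, radiotherapy (except palliative radiotherapy), immunotherapy, biologic or hormonal therapy for cancer treatment".

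Four other provisions bear on how the two are read.

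- Section 5 requires each patient to meet "none of the exclusion criteria for this study at the time of allocation in each cohort of the study".
- Section 6.5.1 lets investigators give treatment "deemed necessary to provide adequate prophylactic or supportive care except for those medications identified as" excluded in 6.5.2.
- Item 4 of the 6.5.2 list has its own DLT-period limit: "Prophylactic antiemetic premedication for nausea or granulocyte colony stimulating factors is not permitted during the DLT Evaluation period".
- Section 6.6.2 makes a subject DLT-evaluable on two planned doses plus completed safety follow-up, or on having a DLT. On attribution it says: "Toxicity that is clearly and directly related to the primary disease or to another etiology is excluded from this definition".

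**The concern.** Exclusion 17 shows that the sponsor meant to keep palliative local treatment out of the period that decides dose escalation. Section 6.5.2 is where a site looks once a subject is being treated, and it does not carry that limit. A site could follow item 2 to the letter and give radiotherapy in the first 28 days.

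What is at stake is the clarity of the DLT assessment. Section 6.6.2 lists grade 3 or worse pneumonitis or ILD as a DLT, and also grade 3 or worse diarrhoea that does not settle on maximal supportive care. A chest or pelvic field could produce similar events. The SRC would then have to decide whether the product or the radiotherapy was the cause. An error could go either way: a product toxicity put down to radiotherapy, or a radiotherapy toxicity counted against the dose.

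Under Section 6.6.1 these calls carry weight. No DLT in three subjects passes the cohort, one in three expands it to six, and two or more stop it. One attribution can move a cohort from one branch to the next.

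**Working it through.** No arithmetic applies: the plan gives no figure on this point, and the check is a comparison of texts.

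**Step 1. The two rules side by side.**

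| Condition on palliative radiotherapy | Exclusion 17 (5.2) | Item 2 (6.5.2) |
|---|---|---|
| Timing | Only after the DLT-evaluation period | None stated |
| Study Physician | Prior consultation and agreement | None stated |
| Extent | Isolated lesions | None stated |
| Reference to the other rule | None | None |

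**Step 2. Which rule a site would apply on treatment.** Section 5 ties the exclusion criteria to allocation. Section 6.5.1 directs prescribers to 6.5.2, and 6.5.2 describes itself as governing the study period. Item 2 states an express exception, so a reader of that list sees no gap that would send them back to the entry criteria. Item 4 of the same list names the DLT period. Its absence from item 2 therefore reads as no limit.

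**Step 3. What happens to a subject irradiated in the window.** The window runs to 28 days after dose 1 or 14 days after dose 2, whichever is later. The evaluability definition in 6.6.2 asks about doses received and follow-up completed, not about concurrent local treatment. The subject stays in the denominator. The case-by-case SRC review in Section 6.6.3 concerns subjects started in error against the selection criteria, so it does not cover this subject.

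**Step 4. Whether another safeguard would bring it to light.** The sponsor notification in 6.5.2 applies to the prohibited therapies on the list. Palliative radiotherapy is excepted, so on the present wording it need not be notified. Section 6.5 requires recording of medications and vaccines, and radiotherapy is not clearly either. The SRC reviews all available safety and PK data (Section 6.6.3), but nothing in these sections ensures that in-window radiotherapy is among them. The case is not hypothetical to the protocol: Appendix E tells sites how to handle a target lesion that receives radiotherapy during the study.

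**Result.** For the same treatment in the same window, exclusion 17 says no and item 2 says yes.

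**The case against.** The strongest reply is that the two rules can be read together. Exclusion 17's timing clause only makes sense on study, since no DLT period exists at allocation, and a site that obeys the stricter text breaks neither rule. On that reading only a cross-reference is missing. The point about the clause's meaning is fair, and it confirms the sponsor's intention. It does not settle what a site will do, because the clause sits among the entry criteria while the list written for on-study use grants the exception outright.

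The reply is also right that the misattribution route is narrow. Section 6.6.2 removes only toxicity that is clearly and directly due to another cause, so an event of doubtful origin stays eligible as a DLT. SRC judgement, including DLT definition 11, gives further protection. A reader might infer that any toxicity after radiotherapy would drop out of the DLT count; the wording does not allow that.

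A reader might also infer that item 3 has the same fault, since it says that temporary "corticosteroids for treatment of underlying or concurrent illness or in the setting of palliative radiotherapy may be permitted upon discussion with the Study Physician" and gives no time limit. The documents do not support this. Exclusion 17 says nothing about corticosteroids as cover for radiotherapy, and item 3 already requires discussion with the Study Physician, who (or whose delegate) chairs the SRC. A new time limit there would be an added restriction, and it would close the stated route to steroid cover when radiotherapy is urgent. Steroids for intercurrent illness pass through the same discussion and conflict with no other rule.

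**Conclusion.** The inconsistency stands, for item 2 only. It is a rule that is wrong as written, because it permits what another current section of the same protocol rules out in the DLT window. Severity is minor.

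The conclusion on the texts needs no assumption. The consequence depends on a subject needing palliative radiotherapy in Cycle 1 and then having a toxicity that both causes could explain. That should be uncommon, but with 3 to 6 evaluable subjects per cohort a single such case could bear on the decision.

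A reader might want to turn this into a bias in the probability that a cohort passes. The documents give neither an expected DLT rate nor a frequency of in-window radiotherapy, and the direction of any error is open. Any such figure would rest wholly on assumed inputs, so none is offered.

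**What to change.** Amend the exception in Section 6.5.2 item 2 to read: *radiotherapy (except palliative radiotherapy of isolated lesions after the DLT-evaluation period, with prior consultation and agreement of the Study Physician)*.

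Radiotherapy inside the window then counts as a prohibited therapy. If it is clinically urgent it is still given, but it triggers the sponsor notification that 6.5.2 already requires, and the sponsor can put it before the SRC for the cohort decision. Leave item 3 and the evaluability definition in 6.6.2 as they are.

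The cost is one phrase in a protocol amendment, with no extra subjects, visits or assessments. The limit is one the sponsor has already written in exclusion 17.

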6.6 Dose modification

6.6.1 Starting dose, dose escalation scheme and stopping criteria

Subject will receive MEDI9447 via IV infusion at a starting dose of 1500 mg.

Rules for Dose Escalation

- 1 Subjects who do not meet the criteria for the DLT-evaluable subject will be replaced. Subjects will be followed for safety throughout the study. If late emerging imAEs (imAEs occurring after the DLT-evaluation period) are observed, these events will be considered by the SRC during data reviews.
- 2 Intra-subject dose escalation will not be allowed.
- 3 A minimum of 3 evaluable subjects will be enrolled in each dose-level cohort. If no DLTs are observed in the first 3 subjects during the DLT evaluation period and all available

safety data have been reviewed by the SRC, dose escalation will continue to the next dose cohort at Cohort 1 or stop and be decided as a tolerated dose at Cohort 2.

- 4 If 1 of 3 evaluable subjects in a dose-level cohort experiences a DLT, that dose-level cohort will be expanded to a total of 6 evaluable subjects. If no more than 1 of 6 evaluable subjects in the dose-level cohort experiences a DLT, dose escalation will continue to the next dose-level cohort at Cohort 1 or stop and be decided as a tolerated dose at Cohort 2.
- 5 If unacceptable toxicity is encountered or ≥ 2 subjects experience a DLT at dose-level cohort then the dose-escalation should be terminated and no more subjects will be entered in that cohort.
- 6 Intermediate or lower dose levels of MEDI9447 may be evaluated at the discretion of the sponsor based on available data.

6.6.2 Definition of dose-limiting toxicity and evaluable subject

DLT evaluable patients are defined as those who received 2 planned doses of MEDI9447 per protocol during the DLT assessment period and completed the safety follow-up through the DLT assessment period, or those who experienced a DLT. Also, the period for DLT evaluation is defined as the time from receiving the first dose of investigational product until assessments prior the planned administration of the third dose; this corresponds to 28 days after receiving the first dose of the investigational product or 14 days after the second dose, whichever occurs later (defined as Cycle 1). Subjects who do not remain in the study up to this time for reasons other than DLT will be considered non-evaluable for DLT assessment and will be replaced with another subject at the same dose level. In case of discontinuation from or interruption of treatment due to AE during the DLT evaluation period (e.g., \geq grade 3 IRR), whether the AE should be a DLT will be discussed by the SRC based on the below mentioned DLT definition 11. Grading of DLTs will be according to the NCI CTCAE v4.03.

A DLT will be defined as any of the events listed below that occurs during the DLT-evaluation period (defined above). Toxicity that is clearly and directly related to the primary disease or to another etiology is excluded from this definition. The following will be DLTs:

- 1 Grade 4 immune-mediated adverse event (imAE)
- 2 \geq Grade 3 colitis
- 3 \geq Grade 3 nausea, vomiting, or diarrhea that does not resolve to Grade 2 or less within 3 days of the initiation of maximal supportive care
- 4 \geq Grade 3 pneumonitis or ILD
- 5 Grade 4 anemia or anemia requiring red cell transfusion
- 6 Grade 4 thrombocytopenia or neutropenia that is present for more than 4 days
- 7 Grade 3 thrombocytopenia with bleeding or thrombocytopenia requiring platelet transfusion

- 8 Febrile neutropenia
- 9 Isolated liver transaminase elevation $\geq 5 \times$ but $\leq 8 \times$ ULN or isolated total bilirubin $\geq 3 \times$ but $\leq 5 \times$ ULN that does not downgrade to Grade 2 or less within 14 days after onset with optimal medical management, including systemic corticosteroids. Isolated liver transaminase elevation $> 8 \times$ ULN or isolated total bilirubin $> 5 \times$ ULN regardless of duration.
- 10 Increase in AST or ALT $> 3 \times$ ULN and concurrent increase in total bilirubin $> 2 \times$ ULN (Hy's Law) without evidence of cholestasis or alternative explanations (e.g., viral hepatitis, disease progression in the liver)
- 11 Any other toxicity that is greater than that at baseline, is clinically significant and/or unacceptable, and is judged to be a DLT by the SRC

A DLT excludes the following:

- 1 Grade 3 endocrine disorder (thyroid, pituitary, and/or adrenal insufficiency) that is manageable with or without systemic corticosteroid therapy and/or hormone replacement therapy
- 2 Grade 3 inflammatory reaction attributed to a local antitumor response (e.g., inflammatory reaction at sites of metastatic disease, lymph nodes, etc) that resolved to \leq Grade 1 within 30 days
- 3 Vitiligo or alopecia of any AE grade
- 4 \geq Grade 3 lymphopenia
- 5 Grade 3 fever
- 6 Isolated laboratory changes of any grade without clinical sequelae or clinical significance that are not defined as a DLT above.

ImAEs are defined as AEs of an immune nature (i.e., inflammatory) in the absence of a clear alternative etiology. In the absence of clinical abnormality, repeat laboratory testing will be conducted to confirm significant laboratory findings prior to designation as a DLT. Late-emerging imAEs (imAEs occurring after the DLT-evaluation period) will be considered by the SRC during data reviews.

